Non-profit observational study on the role of the community pharmacist and services pharmacy in the case management of patients suffering from atrial fibrillation and being treated with new generation oral anticoagulants.

1.1 Study background and rationale

Atrial fibrillation is one of the most common cardiac arrhythmias, from which, in Italy, more than a million people are affected and estimates speak of an increase of up to 70% in the coming years. Due to its ability to increase the thrombo-embolic risk, the affected people are subjected to anticoagulant and antiarrhythmic pharmacological interventions in order to protect the patient from highly disabling events such as cerebral stroke or other arterial embolisms.

However, these pharmacological therapies require a dynamic approach over time, as the choice of active ingredients and the relative dosages depend on the patient's overall health status and for this reason it is important that he adheres to the monitoring plan, prepared by the Specialist in Cardiology, so that therapeutic appropriateness is always guaranteed.

In daily clinical practice, the follow-up activities, defined by the guidelines of the European Society of Cardiology (ESC), consist in the evaluation of:

- General health status
- Bleeding events and related risk
- Therapeutic adherence
- Kidney function
- Drug interactions
- Control of heart rhythm and related symptoms
- Progression of the pathology

In the recent past, these activities were carried out only and exclusively by the Specialist in Cardiology, as the only person authorized to prescribe the new oral anticoagulant drugs. Only recently, with the introduction of the AIFA 97 note, the General Practitioner was given the

opportunity to prescribe these drugs to the patient suffering from Non-Valvular Atrial Fibrillation and to carry out the necessary monitoring. Consequently, the visit to the Specialist is reduced to once a year or whenever the General Practitioner deems it appropriate.

However, the recent epidemiological emergency has highlighted the need to redesign the follow-up pathways of these patients in order to reduce interpersonal contacts today and to simplify those pathways tomorrow. In fact, nowadays, patients suffering from atrial fibrillation and on anticoagulant therapy must carry out a series of interminable steps to comply with all the activities provided for in their follow-up plan. This, as the National Health System is organized today, therefore, translates into a lose-lose scenario, due to the lack of reconciliation between the diagnostic and therapeutic activities to be carried out and the rhythms of life.

On the basis of this, it is necessary to design follow-up models, which, thanks to the territorial integration of all the care settings and the related health professionals available, allow the patient to be able to enjoy 0 km assistance models, which allow him to carry out the activities provided for in the treatment plans in the simplest and most immediate way possible in order to be able to guarantee in a timely manner the most suitable treatments for your state of health, foreseeing and preventing complications and responding effectively and efficiently to the needs emerging.

Among the health professionals available to date, that of the Community Pharmacist is little considered, which represents, due to the position in which it is located within the National Health Service, a potential that has not yet been fully exploited. In fact, he could take on the role of case manager (professional who manages one or more cases entrusted to him according to a predetermined path, such as the PDTA, in a defined space-time context) of the patient suffering from atrial fibrillation and in therapy with oral anticoagulants of new generation thanks to the capillarity on the territory, the hourly availability higher than any other territorial health facility, the health skills in its possession and what it can offer in terms of services within the so-called "services pharmacy". In this scenario, the pharmacist would not replace any of the other actors already present in the multidisciplinary care team but would integrate into it and, moreover, being already affiliated with the National Health Service, the conferral of this role would not cause a excessive cost increases, such as that which would result from hiring new staff to achieve the same goals. The involvement of community pharmacists in the case management of these patients could represent the "sustainable" key for de-hospitalization of chronic patients, which has been talked about for some time without being able to find concrete and at the same time not particularly costly solutions, and the gateway to

the National Health Service that allows them to monitor their state of health, be supported in their activities and remain connected with all the other actors in the care process.

2. Literature review

After confirming the diagnosis, the patient with non-valvular atrial fibrillation is subjected to anticoagulant and antiarrhythmic drug therapy (1-2). Usually, for this therapeutic indication, new generation oral anticoagulant drugs based on edoxaban, rivaroxaban, apixaban and dabigatran are used.

When these drugs were introduced as an alternative to the now well-known warfarin, their spread was very fast due to the non-need for continuous blood monitoring and the fewer drug-food and drug-drug interactions.

However, it soon became evident the need to develop new monitoring models, which even if with a lower frequency than those used for warfarin, would allow an evaluation over time of the therapy practiced to confirm or not the appropriateness, safety and effectiveness. In this regard, in countries where there is already a widespread use of the electronic health record, studies were immediately conducted on what could be the elements to monitor and reassess during the follow-up phase through the implementation of dedicated dashboards (3) and ad hoc protocols in order to expand the services provided by anticoagulation clinics (4).

In defining the follow-up plans for this type of patient, much attention has always been placed on renal function (5) and the related haemorrhagic consequences. In fact, people with renal insufficiency are more at risk of haemorrhagic and / or thrombo-embolic events and this risk increases over time. For this reason, a continuous reassessment of renal function is necessary to ensure that the patient is constantly given the correct dose of the anticoagulant (6).

The activity of community pharmacists is particularly useful for this purpose, as evidenced by numerous evidences in the literature. In fact, the intervention of the community pharmacist allows, thanks to continuous contact with patients and specific training received, to ensure the appropriateness, safety and effectiveness of the drug therapy practiced (7-13).

However, the involvement of community pharmacists is the result of care models that provide for the complete integration of the various actors involved. Scenarios of this type are now consolidated in various countries of the world, while in Italy they still struggle to have a full realization.

With regard to the monitoring of the disease, no innovative follow-up models have been found in the literature, which are therefore based on the classic specialist check-up visit.

3. Objectives of the study

Primary Endpoint

The primary objective of the study is to describe the implementation and outcomes of an innovative Smart Clinic model useful for the clinical and pharmacological monitoring of the patient suffering from non-valvular atrial fibrillation treated with new generation oral anticoagulants, in which a community pharmacist, adequately trained, takes on the role of case manager and the patient has the possibility to perform the checks provided in telemedicine and in self-analysis, in the services pharmacy regime, the results of which will be shared in real time with the treating physician and reference specialist of the same.

Secondary Endpoints

The secondary objectives of the study are:

- assessment of adherence to the required controls;
- assessment of the prescriptive appropriateness of the dosages and molecules used;
- assessment of adherence to prescribed therapy;
- assessment of the occurrence of pharmacological problems related to drug-drug interactions;
- assessment of the occurrence of bleeding and / or thrombo-embolic complications;
- evaluation of the acceptance by the General Practitioner and / or the Specialist in Cardiology of the reports made by the pharmacist and the subsequent actions taken;
- assessment of the economic and social impact of this model on the National Health Service and on the patient;
- assessment of the impact on quality perceived by patients in carrying out this innovative monitoring process.

4. Study Procedures

The study, whose duration will be equal to 12 months (September 2021 - August 2022), which does not include any cost for the National Health Service and for the participating patients themselves, is of the following type:

- observational,
- perspective,
- monocentric,
- no profit.

The main phases of the research project are indicated below.

Phase 1: Patient enrollment (September 2021)

In the first phase, lasting a total of one month, patients are enrolled, with the characteristics indicated below, in a number equal to 50.

Phase 2: Review, database validation and definition of Individual Care Plans (September 2021)

In September 2021 we proceed with the validation of the database and with the definition, by the general practitioners involved, of the Individual Care Plans.

Phase 3: Case Management and follow up (September 2021 - August 2022)

In the remaining months, the Case Manager follows the patients in carrying out the checks required by the guidelines in force, relating to non-valvular atrial fibrillation and concomitant anticoagulant therapy, and by the Individual Care Plan drawn up by the attending physician, in case a personalization of the path is necessary. follow-up dictated by the patient's particular clinical conditions (e.g. impaired renal function). 12-lead ECG (performed with Micotel BT electrocardiograph and reported by the HTN Srl control unit), Holter ECG (performed with Cardioline WALK400H and reported by HTN Srl) self-analysis (hemoglobin, hematocrit and creatine, performed with the Allegro device from Nova Biomedical Italia Srl) will be carried out directly in the pharmacy through the use of the equipment and reporting platforms mentioned above. The control of drug interactions will be performed using the INTERcheck Web platform of the Mario Negri IRCCS Institute for Pharmacological Research.

The follow-up agenda includes the following activities:

Timing	Attività	Note
Enlistement	General health status	
	Pharmacological Therapy	- evaluated at each therapeutic insertion
	12-lead ecg	
	Dynamic ecg sec. Holter	- if not performed within the previous 12 months - if in the FVM ecg > 90 or <60bpm during AF
	Blood chemistry tests	
	Blood pressure and heart rate	
Frequency Monthly	General health status	
	Blood pressure and heart rate	
	12-lead ecg	- if specific symptoms are reported
Quarterly frequency	Single-track ecg	
	Blood chemistry tests	- if clearance ratio creatininemia / 10 = 3
Six-monthly frequency	12-lead ecg	
	Blood chemistry tests	- if patient over 75 and patients with cl cr/10 = 6
Annual frequency	12-lead ecg	
	Dynamic ecg sec. Holter	
	Blood chemistry tests	

After each follow-up meeting, a report including all the measurements made will be sent, through a special telemedicine platform, to a cardiology specialist for an initial analysis. The latter, after a careful evaluation of the documentation received, will forward a feed-back report with any

suggestions for the treating physician and / or the reference specialist, who, based on the knowledge of the patient in question, will define the actions to be taken. .

For the requested services that cannot be carried out in the pharmacy, the pharmacist proceeds with the execution of the prescription from the General Practitioner, the booking of the examination through the CUP service and the execution of a telephone reminder service that reminds the patient when to carry out the 'examination.

5. Expected duration of the study

The study will run for 12 months, from September 2021 to August 2022.

6. Inclusion and exclusion criteria

ARRUOLABLE patients:

- age> 18 years,
- patients suffering from Non-Valvular Atrial Fibrillation and being treated with new generation oral anticoagulants;
- able to express consent to the study;
- regularly related to the trial site (Farmacia [name] S.r.l.)
- AntiCovid19 vaccination performed

7. Case Report Form (CRF)

Electronic data collection forms are provided (Case Report Form - CRF) necessary for the collection of the patient's clinical information, together with those of an organizational and managerial nature.

The detail of the information to be collected is defined in the data collection forms.

For the purpose of a homogeneous data collection, for each patient belonging to the target population, the compilation of a form is envisaged, the structure of which generally includes the following macro-areas:

- general information about the patient (ID, sex, age, etc.);
- information relating to the family setting (spouse, children, care giver, etc.)
- proximate and distant pathological history
- drug therapy practiced

- vital signs and entry blood tests
- examinations and procedures required for follow up
- results and reports of the checks carried out during the follow-up;
- perceived quality questionnaire.

8. Sample size and statistical analysis

A simple size of 50 patients was defined for the conduct of this study.

The statistical analysis of the collected data will be developed through descriptive analysis.

The economic evaluation will be performed by comparing the costs incurred in the traditional path and the costs resulting from the application of the model under study, calculated by referring to the regional tariff where appropriate.

The assessment of the perceived quality will be carried out through a short anonymous questionnaire administered at the end of the study to all the subjects enrolled.

All categorical variables measured in this study will be expressed as absolute numbers and percentages. Continuous variables will be expressed as mean and standard deviation or median and interquartile range [IQR], depending on the normal or non-normal distribution of the data.

Differences will be analyzed by chi-square test, unpaired t-test or Mann-Whitney U test, depending on the nature of the variable.

Any difference with a $p < 0.05$ will be considered statistically significant.

9. Results expected from the study

The patient suffering from non-valvular atrial fibrillation and being treated with oral anticoagulants needs his state of health to be in a condition of equilibrium between the risk of bleeding on the one hand and the risk of thrombo-embolism on the other.

For this reason, it is important that this type of patient undergoes constant checks over time to verify that his clinical conditions are always balanced, however, the daily rhythms of life hinder full adherence to the controls.

This study by overcoming this and other critical issues, thanks to the use of the unexpressed potential of the service pharmacy (remote execution of the services provided by the follow-up paths) and of the pharmacist, as case manager, alongside medicine basic and specialized, will allow to improve the current quality of care for the type of patients examined, with a view to safety, efficacy and appropriateness of care on the one hand and sustainability on the other.

10. Ethical considerations

To protect privacy, patients in the group described above will be identified only by means of progressive numerical codes (ID).

The data will be treated with confidentiality and confidentiality and disclosed only in aggregate and anonymous form.

The protection of individuals will be guaranteed as recommended in the Oviedo Convention (Convention for the Protection of Human Rights and the Dignity of the Human Being with regard to the Application of Biology and Medicine: Convention on Human Rights and Biomedicine - April 4, 1997) and in the Declaration of Helsinki relating to ethical principles for medical research and whose aim is to provide advice to doctors and other participants in medical research.

All patients will be required to sign a written Informed Consent, with particular reference to the processing of personal data.

11. Bibliography

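### Does the cardiologist's first read prevent the study from reporting how physicians accept the pharmacist's reports?

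*Combined protocol and SAP*

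**What the plan says.** Section 3, Secondary Endpoints, lists "evaluation of the acceptance by the General Practitioner and / or the Specialist in Cardiology of the reports made by the pharmacist" and the actions taken afterwards. It gives no criterion for acceptance, no unit (report, issue or patient) and no denominator.

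Section 4, Phase 3, describes the flow of information. Once a visit is over, "a report including all the measurements made will be sent, through a special telemedicine platform, to a cardiology specialist for an initial analysis". The feedback report from that specialist carries any "suggestions for the treating physician and / or the reference specialist, who, based on the knowledge of the patient in question", settle the action. The same section says "The control of drug interactions will be performed using the INTERcheck Web platform", without saying how interaction findings reach a physician.

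The primary objective in Section 3 describes the checks done in the pharmacy, "the results of which will be shared in real time with the treating physician and reference specialist of the same".

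Section 7 says "The detail of the information to be collected is defined in the data collection forms". Its list of macro-areas, offered as a general outline, includes the results and reports of follow-up checks. Section 8 plans a descriptive analysis: "All categorical variables measured in this study will be expressed as absolute numbers and percentages".

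**The concern.** The objective asks how physicians receive the pharmacist's work, but on the Section 4 route a cardiologist reads that work before the treating physician acts. Where the cardiologist adds a suggestion, the action may be a response to the pharmacist, to the suggestion, or to both. The and/or in the objective also joins two responding roles. The term for the cardiologist could mean the first-line reader or the reference specialist, and agreement by the first is a different outcome from action by the second.

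If everything were collapsed into one percentage, a reader could not tell whose input had been accepted. This is the only secondary objective on physicians' response to the pharmacist as case manager, the role at the centre of the primary objective. Source and role are also easier to record as each response occurs than to reconstruct later.

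**Working it through.** The plan gives no figure for this endpoint, so there is none to reproduce. The check compares the passages and then asks what arithmetic can add.

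**1. Are the endpoint's reports the ones routed through the cardiologist?** Section 3 speaks of reports made by the pharmacist. Section 4 speaks of a post-visit report of measurements. No text equates the two. The acceptance objective stands beside objectives on dose and molecule appropriateness, therapy adherence and drug interactions. If the pharmacist flags such matters directly to the General Practitioner, the cardiologist's step does not touch them. The extent of any mixing depends on a link that the documents do not make.

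**2. Does the plan pool sources?** No. The objective counts acceptance of the pharmacist's reports. A suggestion that originates with the cardiologist is outside that wording. Section 8 promises counts and percentages for categorical variables and prescribes no single overall figure.

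**3. What would pooling cost if it happened?** Let A be the pooled acceptance rate and q the share of pooled issues that the pharmacist raised. Both are assumed, since neither is in the documents. Acceptance of the pharmacist's issues then lies between

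- lower bound = max(0, (A − (1 − q)) / q)
- upper bound = min(1, A / q)

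With A = 0.60:

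| q | Lower bound | Upper bound |
|---|---|---|
| 0.5 | (0.60 − 0.50)/0.5 = 0.20 | min(1, 0.60/0.5) = 1.00 |
| 0.7 | (0.60 − 0.30)/0.7 = 0.43 | 0.60/0.7 = 0.86 |
| 0.9 | (0.60 − 0.10)/0.9 = 0.56 | 0.60/0.9 = 0.67 |
| 1.0 | (0.60 − 0)/1 = 0.60 | 0.60/1 = 0.60 |

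The wide ranges come only from letting cardiologist-raised issues into the count. Under the objective as worded, q = 1 and the interval closes on A.

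**4. Can the number of affected reports be found?** Reading the monthly row as one meeting per month from October 2021 to August 2022, with full retention, gives 50 × 11 = 550 follow-up reports. This is a ceiling on traffic. It does not count mixed responses, because the share that draws a suggestion is not stated.

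**5. Can source be told apart with the material described?** Section 4 describes two separate items, the report and the cardiologist's feedback. If both are kept, comparing them can show who raised what. Section 7 leaves item-level content to the forms, so dedicated fields may also exist.

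**6. What would per-issue logging not solve?** If the pharmacist raises an issue and the cardiologist passes it on unchanged, the physician has seen an endorsed message. Logging cannot isolate the response to the pharmacist alone in that case. It is a feature of the care pathway being described.

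**The case for a change.** The strongest case for a change is that the protocol does not settle the matter. It has no definition of acceptance, none of the eight listed CRF areas names the originator, the responder or the decision, and two cardiology roles could fit one term. The real-time sharing in the primary objective does not clearly help: no text says what the physician sees first, and a parallel route could make the source of a response harder to identify. A few fields and a sentence or two would cost little.

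Most of this stands as description. The definition is missing and the term is ambiguous. It does not show a rule that yields a wrong result. The CRF list is a general outline, so absence from it does not show absence from the forms.

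The natural remedy also has a trap. A rate per role with every pharmacist-raised issue in the denominator would count against a physician those issues that the cardiologist dropped, or that went only to the other recipient. That physician might never have received them. A sensible analyst would use the issues that reached each role, and the plan as written allows this.

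The General Practitioner and specialist belong to a multidisciplinary team that the pharmacist is meant to join (Section 1.1). The team's response to a cardiologist-reviewed report is therefore a legitimate outcome of the model in its own right.

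**Conclusion.** No change to the plan is needed. This is a gap in detail that analysts can fill sensibly: say which reports and which cardiology role are meant, present results by responding role over the issues that reached that role, and note that a response to an endorsed issue cannot be credited to the pharmacist alone. The wording of the objective already keeps the cardiologist's own suggestions out of the count.

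The consequence is small. The endpoint is secondary and descriptive in a single-group study of 50 patients, and neither the sample size nor any error rate depends on it. The size and direction of any distortion cannot be derived from the documents.

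This conclusion assumes that the analysis follows the objective as worded, and that either the data collection forms record originator and responder or the pharmacist's report and the cardiologist's feedback are both retained. If neither record were kept, the response could be reported only at team level. That would still describe the model, but would answer this one objective less directly.

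### Does the August 2022 close push the annual checks out of the study and so unsettle the adherence and cost figures?

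*Combined protocol and SAP*

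**What the plan says.** Section 4 gives the duration as "The study, whose duration will be equal to 12 months (September 2021 - August 2022", and section 5 repeats it: "The study will run for 12 months, from September 2021 to August 2022". Enrolment uses the first of those months ("Phase 1: Patient enrollment (September 2021"), and the account of Phase 3 then says "In the remaining months, the Case Manager follows the patients in carrying out the checks required by the guidelines in force".

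The follow-up agenda in section 4 has rows for enlistment and for monthly, quarterly, six-monthly and annual checks. The last is headed "Annual frequency" and lists a 12-lead ECG, a Holter and blood chemistry, all of which also appear at enlistment. No row has an anchor date or a visit window. The only look-back is a note on the enlistment Holter, "if not performed within the previous 12 months". Blood chemistry in the quarterly and six-monthly rows is conditional; the six-monthly note reads "if patient over 75 and patients with cl cr/10 = 6".

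Two secondary objectives in section 3 draw on these checks: "assessment of adherence to the required controls" and the economic impact of the model. Section 8 says that costs in the traditional path and in the model will be compared, without a time horizon, and that the data will be analysed descriptively.

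**The concern.** Enrolment falls inside the 12 months, so no patient is followed to a full calendar anniversary. If the annual row means 12 months after enlistment, it is never reached. If it means once in the study year, a second set of the three tests is expected by August 2022. The text does not choose between the two.

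The choice could affect three things:

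- **Adherence:** whether three more items per patient enter the denominator.
- **Costs:** whether the model carries one or two sets of these tests.
- **Blood tests:** if the annual row drops out, a patient who meets neither blood-test condition would have no scheduled blood test after enlistment, unless the Individual Care Plan adds one.

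In a study whose output is descriptive, a counting rule can move the reported result, so the point deserved a check.

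**Working it through.** **Inputs.** Study period and enrolment month come from sections 4 and 5, agenda rows from section 4, and the 50 patients from section 8. The documents give months only, so enrolment on 1 to 30 September 2021 and close on 31 August 2022 are assumptions.

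**1. The plan's own figure.** 1 September 2021 to 31 August 2022, both days included, is 365 days. The stated 12 months reproduces.

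**2. Follow-up and the 12-month date.**
- Enrolled 1 September: 364 elapsed days to close; anniversary 1 day after close.
- Enrolled 30 September: 335 elapsed days; anniversary 30 days after close.

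The result depends somewhat on the day count:

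| Convention | 12-month date relative to close | Enrolment days past close |
|---|---|---|
| Calendar anniversary or +365 days | 1 to 30 days after | 30 of 30 |
| +364 days (enrolment is day 1) | 0 to 29 days after | 29 of 30 |
| 12 x 30 = 360 days | 4 days before to 25 days after | 25 of 30 |

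**3. Items due by close, counted from enrolment.** There are 11 monthly dates, 3 quarterly, 1 six-monthly and 0 annual. For a patient with no blood-test trigger, leaving out symptom-driven ECGs:

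11 x 2 (general health; blood pressure and heart rate) + 3 (single-track ECG) + 1 (12-lead ECG) = 26 items.

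The annual row adds 3, giving 29.

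**4. Adherence of a patient who does everything due.**
- Annual set expected before close: 29/29 = 100%.
- Annual set not yet due: 26/26 = 100%.
- Holter alone falling due in the study because the last one preceded enlistment: 27/27 = 100%.
- Mixed rule (planned as not due, scored as expected): 26/29 = 89.7%.
- Mixed rule extended to every month-12 item: the denominator is 24 monthly + 4 quarterly + 2 12-lead ECG + 1 Holter + 1 blood = 32, so 26/32 = 81.3%.

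The last two figures take the numerator from one reading and the denominator from the other. The 81.3% also brings in monthly and quarterly items, which are a separate matter from the annual row. All of these figures assume item-level scoring, which the plan does not specify.

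**5. Costs.** For the same patient, 12-lead ECGs, Holters and blood tests, enlistment included:
- With an enlistment Holter: 2 + 1 + 1 = 4 without the annual set, 3 + 2 + 2 = 7 with it.
- Without one: 2 + 0 + 1 = 3, or 3 + 1 + 2 = 6.

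The difference is 3 tests per patient, so at most 50 x 3 = 150. This counts the model path only. Section 8 calls for a comparison of two paths. If the annual set is counted in both or left out of both, the contrast changes by the difference in cost between the paths for those tests, not by their full cost.

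**6. Blood tests.** The number of patients with no trigger is not in the documents, so the number with no scheduled blood test after enlistment cannot be derived. It arises only if the annual row is taken as falling after close.

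**The case for a change.** The strongest case for a change is that descriptive figures are this study's main output, that no adherence denominator or cost horizon is stated, and that a few sentences would supply both. The Individual Care Plans and data collection forms might set due dates, but the protocol does not say that they do. Enlistment already includes an ECG and blood chemistry, so it is not self-evident that the annual row asks for another set.

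The missing anchor, window and cost horizon are real, and the date arithmetic is right under its assumptions. The inference to an unreliable result does not follow. An annual row in an agenda written for a 12-month study would be pointless if it could never be carried out; one set within the study year is the plain reading. Section 7 also gives the case report form one area for the examinations follow-up calls for and another for the findings of checks actually done. Those are plausible sources for the denominator and numerator, although the forms themselves were not available to confirm it.

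**Conclusion.** No change to the plan follows. This is missing detail that analysts would fill sensibly: count as required what was due by a patient's last data date, and compare both cost paths over the same period. No stated rule produces a wrong figure. Applied consistently, either reading gives a fully compliant patient 100%. The annual set amounts to 3 of 29 items per patient and at most 150 tests in the model path, with the net effect on the cost contrast not derivable from the documents.

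The results concerned are descriptive and secondary, and neither the sample size nor any decision rests on them. The 1 to 30 day gap depends on enrolment across 1 to 30 September, close on 31 August and an anniversary count from enrolment. Other day counts shift it by a few days without altering the conclusion. What would reverse it is evidence that the annual checks are to be scheduled after close and still scored as missed; nothing in the documents suggests that.
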